# Proposed Protocol

## Phase 1- Weeks 1 to 2

- Quad Set: 10 second on, 10 second rest at 100% occlusion x10'
  - progress to isometrics at the edge of the table 60 degrees as clinically appropriate
- Side Lying Hip Abduction, 30/15/15/15, at 80% occlusion
- Hip Extension from prone 30/15/15/15, at 80% occlusion
- Re-check load at the start of each Phase, to determine 1 RM (7-10RM test on leg press)
- Total BFR time approximately 24 minutes per session, with 2 sessions per week

## Phase 2- Weeks 3 to 4

- Replace Quad Set with Long Arc Quad (90-30deg), 30/15/15/15 at 80% occlusion
- Replace Hip Extension with Leg Press (shuttle), 30/15/15/15 at 80% occlusion
- Hip Abduction, 30/15/15/15 at 80% occlusion
- Total BFR time approximately 24 minutes per session with 2 sessions per week

## Phase 3- Weeks 5 to 6

- Long Arc Quad (90-30deg), 30/15/15/15 at 80% occlusion
- Leg Press (shuttle), 30/15/15/15 at 80% occlusion
- Replace Hip Abduction with Bilateral Hip Bridge, 30/15/15/15 at 80% occlusion
- Total BFR time approximately 24 minutes per session, with 2 sessions per week

## Phase 4- Weeks 7 to 8

- Leg Press (shuttle), 30/15/15/15 at 80% occlusion
- Replace Long Arc Quad with Step Up 30/15/15/15 at 80% occlusion
- Bilateral Hip Bridge, 30/15/15/15 at 80% occlusion
- Total BFR time approximately 24 minutes per session, with 2 sessions per week

## Phase 5- Weeks 9 to 12

- Replace Bilateral Hip Bridge with Medial Step Down, 30/15/15/15 at 80% occlusion
- Replace Step up with Split Squat, 30/15/15/15 at 80% occlusion
- Leg Press (shuttle), 30/15/15/15 at 80% occlusion
- Total BFR time approximately 24 minutes per session, with 2 sessions per week

## Phase 6- Weeks 11 to 12

• Progressively load exercises from phase 5

Total BFR time approximately 24 minutes per session, with 2 sessions per week

a. At the conclusion of each exercise completed listed in the proposed protocol above, the following will be recorded:

i) patient rating of perceived exertion (RPE) will be recorded in the exercise flow sheet.

ii) Ability or inability to complete the exercise session

b. At the conclusion of each treatment session any side effect, as previously described by Brandner et al, 2018, will be recorded in the patient chart.

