## **Previous Work**

Until recently, previous studies have examined the use of BFR with respect to muscular strength, endurance and hypertrophy. With the rise in popularity of BFR, there has been increased attention to overall safety issues of training with BFR. The potential risks to the cardiovascular system that have been considered are increased blood pressure responses, thrombolytic events and damage to the vascular system [10].Despite these concerns, there have been several extensive reviews published demonstrating that the side effects are minimal [10, 11, 12], and that training with BFR and when compared with traditional methods shows no greater risk [13]. Additionally, a closer look at the literature has demonstrated that the use of BFR has shown significant strength adaptations in multiple patient populations:

- A 2017 study showed a 2-fold improvement in extension and flexion strength with the use of BFR in patients after knee arthroscopy [15].
- Patients with patellofemoral pain had greater improvements in knee extension strength following the use of BFR training [14].
- A 2003 study demonstrated improved quadriceps strength with BFR training in patients after ACL reconstruction [16].
- Greater improvements in thigh circumference as opposed to a standard group [17].

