## Purpose of the Research, Specific Aims and Hypotheses

The purpose of this study is to determine the safety and efficacy regarding the addition of BFR-based exercise to traditional methods of physical therapy in the adolescent, post-surgical population.

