### Secondary aim:

- 1. To determine the impact of adding BFR training during post-surgical rehabilitation on patient reported outcomes.
  - a. We hypothesize that BFR training will show greater patient reported outcome scores on the post-op when compared to a control group.
- 2. To determine the impact of adding BFR training during post-surgical rehabilitation on hypertrophy and mid-thigh circumference.
  - a. We hypothesize that BFR training will demonstrate significant increased mid-thigh circumference over measured time points.
- 3. To determine and record patient tolerance and reported side effects and to BFR training during postsurgical rehabilitation.
  - a. We hypothesize that patient tolerance to BFR will be consistent with previously published literature.

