## **Functional Outcome Definitions/Data Points Collected**

- 1. Demographic information will be collected and outcome measures will include the following:
  - a. Age
  - b. Medical record number
  - c. Date of ACL surgery and related surgeries
  - d. Sex
  - e. Graft Type
  - f. Surgeon
  - g. Sport
  - h. Level of competition in sport
  - i. Weight and Height
  - j. BMI
  - k. Weight bearing precautions (weeks)
  - 1. Limb length (cm): ASIS to superior medial malleolus
  - m. Tegner Scale
- 2. Opened or closed Physis (or skeletal maturity)

3. Data will be collected at five different time points during the rehabilitation process. The current standard of care includes a pre-operative visit, a 3-month assessment visit, and a return to sport visit between 6-9 months post-operative, and a1 year follow up. Additionally, we will collect data a 2 year phone/email follow up to record patient outcomes. These assessments are completed in conjunction with the surgeon's follow up visit. The physical therapist completing the assessment will record the outcomes in a secure Excel data collection form.(or Access data base)

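### Side effects have one scheduled collection point, the end of each treatment session, with no look-back question and no item at later contacts, so some events may be under-recorded

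*Combined protocol and SAP*

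**What the plan says.** Purpose of the Research sets out to "determine the safety and efficacy regarding the addition of BFR-based exercise". Secondary aim 3 is "To determine and record patient tolerance and reported side effects", with the hypothesis that tolerance will match published literature. No rate or margin is given for that comparison, and the Data Analysis section describes no analysis of side effects.

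Under Previous Work, the cardiovascular risks considered are "increased blood pressure responses, thrombolytic events and damage to the vascular system". The same section cites reviews that found minimal side effects and no greater risk than traditional methods.

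The collection rule is item b at the end of Proposed Protocol: "At the conclusion of each treatment session any side effect", of the kinds described in one cited 2018 paper, "will be recorded in the patient chart". The paper's list is not reproduced. Item a adds perceived exertion and whether the exercise session could be completed.

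The BFR schedule is "Total BFR time approximately 24 minutes per session, with 2 sessions per week", ending with "Phase 6- Weeks 11 to 12".

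Patient Reported Outcomes and Functional Outcome Definitions/Data Points Collected list what is gathered before surgery, at 3 months, at return to sport (6 to 9 months), at 12 months and at 2 years. On the last of these the plan says "we will collect data a 2 year phone/email follow up to record patient outcomes". None of the lists has a side-effect or adverse-event item.

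The Retention paragraph requires attendance at 90% of visits for inclusion in the study.

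**The concern.** A record made as a session closes is good at catching what the patient feels then. It catches other events only if the patient volunteers them or the therapist happens to ask. The plan leaves three gaps:

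- **Between sessions.** No question covers the days since the last session, so reporting depends on the individual patient and therapist.
- **Events that end attendance.** A patient who stops coming has no next session at which to report why, and the 90% rule may then remove that patient from the study.
- **After the last BFR session.** No later contact lists the item, although four later contacts are already planned.

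The reference to a single paper adds an ambiguity. If it is applied as a checklist, a reaction that is not on it has no clear place in the record. The Background section gives limited adolescent information as the reason for the study, so this group is where an unlisted reaction would be most informative.

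At stake is the meaning of a statement that BFR was well tolerated. Incomplete capture can only lower the observed event rate relative to the true one.

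**Working it through.** The plan states no event rate, power or sample size for side effects, so there is no figure of its own to reproduce. The check compares the collection rule with the contact schedule, then shows what incomplete capture does at this sample size.

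**1. Reporting occasions during treatment.** 12 weeks × 2 sessions = 24. Phase 5 (weeks 9 to 12) and Phase 6 (weeks 11 to 12) overlap. If both were delivered in full, the phase lengths add to 2 + 2 + 2 + 2 + 4 + 2 = 14 weeks, or 28 sessions. The documents need to reconcile this; it does not alter the point.

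**2. Time with no listed collection.** Taking item b to apply to BFR sessions only, and counting weeks from surgery:

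- to one year: 52 − 12 = 40 of 52 weeks (77%)
- to two years: 104 − 12 = 92 of 104 weeks (88%)

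These are lengths of time, not shares of events missed.

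**3. Contacts that could close the gap.** Three months is 52/4 = 13 weeks, so that visit falls about one week after week 12. Return-to-sport testing at 6 to 9 months (26 to 39 weeks) falls about 14 to 27 weeks after it.

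**4. The attendance rule.** If the 90% is applied to 24 BFR sessions (an assumption, since the rule speaks of patient visits generally), missing two leaves 22/24 = 91.7%, and missing three leaves 21/24 = 87.5%, below the threshold. A patient who withdraws early because of side effects would fall out of the tolerance result.

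**5. Effect of incomplete capture.** Let n be the number treated, p the true risk per patient and c the share of events captured. The expected observed rate is p × c, and the chance of recording at least one event is 1 − (1 − p × c)^n. The plan gives n = 33 for the BFR group, and n = 20 as the number with one-year follow-up at which the study ends. The values of p and c are assumptions; the documents give neither.

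| n | p | c = 1 | c = 0.5 | c = 0.25 |
|---|---|---|---|---|
| 33 | 2% | 49% | 28% | 15% |
| 33 | 5% | 82% | 57% | 34% |
| 20 | 5% | 64% | 40% | 22% |

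For a commoner event with p = 10% and n = 33, the expected count is 33 × 0.10 = 3.3 at full capture and 1.65 at half, so the observed rate falls from 10% to 5%.

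**6. Limit set by sample size alone.** With full capture and zero events, the one-sided 95% upper limit is 1 − 0.05^(1/n): 8.7% for n = 33 and 13.9% for n = 20.

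**The case against.** The strongest reply is that item b covers any side effect and sets no onset window. With two sessions a week, a symptom that starts between sessions can be reported within days. This stands. A reader might infer that between-session events are lost; the text supports only that no look-back is specified and capture is not standardised. The reply does not help a patient who stops attending.

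Item b also refers to treatment sessions, not BFR sessions, and rehabilitation can last up to 12 months. Recording might therefore continue after week 12. That reading is possible, but item b sits under the BFR schedule and nothing says that it extends further.

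Other stronger readings are tempting and unsupported:

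- **That thrombotic events will be missed.** The protocol's word is *thrombolytic*. Reading it as thrombotic is a natural inference in a list of possible harms, but still an inference. Nothing in the documents says when such events appear or that delayed events are the more serious ones.
- **That cuff time measures the gap.** 24 × 24 minutes = 9.6 hours, about 0.5% of the 2,016 hours in 12 weeks. This describes exposure. It says nothing about ascertainment, because a report at a session can cover the days before it.
- **That the comparison with the literature must be too favourable.** Published rates may rest on similar session-based recording, in which case the two would be alike. The documents do not say.
- **That only acute discomfort is assessed.** Item a also records exertion and inability to complete the exercise session.

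The cited paper's list may indicate kinds of event and not a closed checklist; its content cannot be judged from the protocol. The contents page names a risks and benefits section, of which only the benefits paragraph was available, so safety text elsewhere cannot be ruled out. The data-collection lists, where a side-effect item belongs, were available and lack one.

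**Conclusion.** The point holds in a limited form. Item b is the only scheduled side-effect collection found. It has no look-back question, depends on one cited paper for its scope, and is not repeated at any later contact. Events that start between sessions, end attendance, or follow the last BFR session may be under-recorded. The likely direction is a side-effect rate that is too low, and so a tolerance result that looks too good. The size is unknown.

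The table shows that at 33 patients the loss could matter: halving capture takes the chance of seeing a 5% event from 82% to 57%. That rests on assumed risks and capture shares and does not estimate what this study will miss. Nor would perfect capture make 33 patients enough to exclude uncommon harms. The change is worth making because safety is a stated purpose and it can be made at contacts already planned.

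**What to change.** 1. Amend Proposed Protocol item b so that at each session the therapist asks one standard question on any new symptom or medical contact since the last session, with onset date, in addition to the end-of-session record.
2. State that any event is recorded, whether or not it appears in the cited paper.
3. Add the same question to the 3-month and return-to-sport data lists, as follow-up after the last BFR session. Adding it at 12 months and 2 years is not recommended: recall and attribution would be weak that long after treatment in patients who also had knee surgery.
4. State in Data Analysis that side effects are reported for every patient who received BFR, whatever their attendance under the 90% rule.
5. Where Previous Work says *thrombolytic*, confirm the intended term.

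This changes data collection and reporting only. It needs no new visit or procedure. The costs are slightly more recording, a somewhat higher reported event rate, and some later events that cannot be attributed to BFR. Prospective controls are to provide the same data points, so a question on the shared visit forms would also give some background rate, though an imprecise one from 14 patients.

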## Sample Size Justification

It is our intention to use all possible patients meeting the inclusion criteria in this study. According to the most recent clinical data available, approximately 100 patients per year receive care for ACL knee injury and 25 to 50 patients per year receive physical therapy at Elite Sports Medicine following ACL reconstruction.

## Accrual and Expected Duration of Accrual

Once approved, we expect that this study can be accomplished within two to three years. The open period for this study will be between January 1, 2020 and December 1, 2023.

## Data Analysis:

The endpoint of this study is when data is collected and analyzed from 20 patients who have completed a one year follow up from date of surgery.

Data will be collected on all patients who meet the inclusion criteria for this study and have agreed to participate through the consenting process. Descriptive statistics will be completed to help gain an overall understanding of the data for the effect of BFR training on lower extremity strength, mid-thigh circumference and outcome measures. T-tests between strength and outcome variables for the BFR and non-BFR group to test if there are differences between the two groups. Correlation tests will be used to determine association between lower extremity strength and BFR training. Corrections will be made for multiple comparisons.

We will be entering into a Data Use Agreement with University of Connecticut (UCONN) for assistance with data analysis and interpretation as well as statistical analysis. All data sharing procedures will be in accordance with Connecticut Children's policy. All data will be de-identified prior to sharing to assure patient's confidentiality. The UCONN collaborator is not engaged in human subject research (no access to identifiers) and will obtain an independent determination from the UCONN IRB.

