## Study Design

The planned pilot study is a prospective study to compare the use of exercises augmented with BFR with quantitative measurements of strength and patient reported outcomes. A total of 33 youth and adolescent patients undergoing a surgical procedure for ACL reconstruction at Connecticut Children's Elite Sports Medicine and completing physical therapy at Connecticut Children's Sports Physical Therapy will be recruited for this study. Additionally, 14 patients will be recruited that do not participate at Connecticut Children's Sports Physical Therapy and do not receive BFR training as prospective controls. Should we be unable to obtain 20 prospective controls, a review of data from 20 previous patients, matched for age, sex, BMI and surgical procedure that completed physical therapy at Connecticut Children's Sports Physical Therapy will be used as a comparison.

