- 6. 12-month testing

Tegner Activity Scale

- 7. Prospective control: All prospective controls will follow the ACL reconstruction protocol at an outside facility. These patients will complete outcome measures, and standardized strength assessments consistent with the standard current standard of care listed above. The same data points will be collected.
- 8. Retrospective controls: Outcome measures (RSI, IKDC) and the results of standardized 3 and 6mo + assessment results will be collected.
- 9. All data points listed above for all three groups will be stored in a Microsoft Excel spreadsheet on the G drive.

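### Recruiting the planned 14 prospective controls always triggers the fallback set at 20, so the comparator is not fixed; separately, the 20-patient end rule names no group

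*Combined protocol and SAP*

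**What the plan says.** Study Design gives the numbers. The BFR group is "A total of 33 youth and adolescent patients undergoing a surgical procedure for ACL reconstruction" who have therapy at the study's own physical therapy centre. In addition, "14 patients will be recruited that do not participate at Connecticut" Children's own therapy service and receive no BFR. The sentence after that sets the fallback: "Should we be unable to obtain 20 prospective controls, a review of data from 20 previous patients", matched on age, sex, BMI and operation and treated at the study's own centre, will serve as a comparison.

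The recruitment section draws these previous patients from billing records for January 2017 to January 2019. The data-collection list has prospective controls supply the same data points as the study group (item 7). For retrospective controls it says (item 8): "Outcome measures (RSI, IKDC) and the results of standardized 3 and 6mo + assessment results will be collected".

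Data Analysis plans t-tests of BFR against non-BFR "to test if there are differences between the two groups". It also sets the end of the study: "The endpoint of this study is when data is collected and analyzed from 20 patients who have completed a one year follow up", counted from surgery. The next sentence reads "Data will be collected on all patients who meet the inclusion criteria for this study" and have consented. Sample Size Justification gives no target number: "It is our intention to use all possible patients meeting the inclusion criteria in this study".

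**The concern.** Two things are unclear: who the BFR patients are compared with, and what ends the study.

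The first matters more. A fallback should apply when recruitment fails. Here the trigger is above the target, so it applies when recruitment succeeds. What it brings in is a different kind of control. Prospective controls are concurrent and have their therapy elsewhere. The previous patients are historical and had their therapy at the study's own centre. Named for them are RSI, IKDC and the 3-month and 6-month-plus assessments; KOOS and MARX are not. With replace or join unstated, the composition of the non-BFR group could be settled after results are seen, in a study that is neither randomised nor blinded.

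The second is that the end rule gives a count without saying whose. A team following it literally could close the study at 20 one-year completers, whichever group they come from, while the rest of the plan points to using everyone.

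**Working it through.** No formula reproduces 33, 14 or 20, because the plan states no effect size, SD, alpha, power or dropout rate. The check is arithmetic on the stated counts.

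**Inputs.** BFR group 33, prospective controls 14, fallback trigger 20 and fallback size 20 (all Study Design); end rule 20 (Data Analysis).

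**Step 1: target against trigger.** 20 − 14 = 6. At full planned recruitment the control group is 6 below the trigger, so the fallback condition is met. The plan would have to exceed its own control target by 6 to avoid it. This needs no assumption.

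**Step 2: size of the non-BFR group**, at full recruitment with no dropout.

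| Reading | Non-BFR patients | √(1/33 + 1/n) |
|---|---|---|
| Target of 14 governs, fallback not used | 14 | 0.319 |
| Previous patients replace prospective controls | 20 | 0.283 |
| Previous patients join them | 14 + 20 = 34 | 0.244 |

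The last column is the standard error of a difference in means in SD units, assuming equal SDs. From the smallest to the largest comparator it falls from 0.319 to 0.244. Taken literally, the trigger leaves only the second and third rows; the first needs the trigger to be treated as a slip. The third row applies only to outcomes that both sources supply.

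**Step 3: the two control sources side by side.**

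| | Prospective | Previous patients |
|---|---|---|
| Period | Concurrent | January 2017 to January 2019 |
| Therapy | Outside facility | Study's own centre |
| Data named | Same data points as the study group | RSI, IKDC, 3-month and 6-month-plus assessments |

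The sources are not interchangeable, so the choice changes what is compared as well as how many.

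**Step 4: end rule against planned numbers.** 33 + 14 = 47. The end rule's 20 equals none of 33, 14 or 47.
- *Prospective controls alone:* not possible as planned, since 20 > 14.
- *Each group:* not possible with 14 prospective controls. It could be met with 20 previous patients only if they have one-year data, on which the plan is silent.
- *Total:* possible, with 47 − 20 = 27 planned patients not required to have reached one year.
- *BFR group alone:* possible (20 of 33), with no requirement on controls.
- *Minimum:* possible, with all 47 still analysed. It agrees with Sample Size Justification and with the sentence after the rule, but it is not written.

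**The case against.** The strongest reply is that the end rule does little harm. Both Sample Size Justification and the sentence after the rule point to using all eligible consenting patients, so 20 is most naturally a minimum, and on that reading nobody is lost. That stands. The end rule is a wording fault whose harm depends on a reading the text does not favour.

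A reader might go further and infer that the analysis is capped at 20 of 47 patients, with a matching loss of precision and power. The documents do not support that. No sentence orders data from other patients to be discarded, and strength and function are measured at 3 months and at return to sport (6 to 9 months), so later enrolees could contribute even if the study ended at the 20th one-year completer.

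A reader might also infer that the previous patients cannot support any one-year comparison. That is not established. In the retrospective-control item, the 3- and 6-month-plus label belongs to the assessment results; RSI and IKDC carry no time limit, and a one-year follow-up is listed as standard of care. What can be said is that KOOS and MARX are not named.

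Nor does storing data for three groups contradict a two-group test: three sources can feed a BFR versus non-BFR comparison. The gap is only how the two control sources are combined.

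It is also fair that the trigger, the fallback size and the end rule all say 20. They agree with one another and conflict with 14, 33 and 47. Matching of the previous patients reduces some differences, but it does not address period or site of therapy. Finally, this is a declared pilot that admits its small sample. That excuses low power; it does not reconcile 14 with 20.

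**Conclusion.** The control figures are wrong as written. With a target of 14 and a trigger of 20, the fallback applies even at full planned recruitment, by a margin of 6. Because replace or join is not stated, the non-BFR group could be 14, 20 or 34 patients, drawn from sources that differ in period, site of therapy and named outcomes. This rests on the stated counts alone; the three sizes assume full recruitment and no dropout.

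The end rule is a lesser, separate fault. It names no group and matches none of the planned numbers. A minimum fits the rest of the plan best and costs no patients, but a literal reading would let the study end before all 47 are followed. No loss of power or precision should be claimed from it.

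**What to change.** 1. In Study Design, make the prospective-control target and the fallback trigger the same number. Setting both to 14 adds no patients; setting both to 20 adds 6 controls. State whether the previous patients replace or join the prospective controls, and for which outcomes, given that KOOS and MARX are not named for them.
2. In Data Analysis, replace the 20-patient sentence with a rule that all enrolled patients in both groups are analysed once each has reached or missed the one-year follow-up. Alternatively, keep 20, say that it is a minimum, and name the group.

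Both are changes of protocol wording. The possible downside is a later analysis date, if the team had meant to analyse as soon as 20 patients completed one year.
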